12 STUDY CONDUCT RESPONSIBILITIES

12.1 PROTOCOL AMENDMENTS, DEVIATIONS AND BREACHES

The CI will seek approval for any amendments to the Protocol or other study documents from the Sponsor, REC and NHS R&D Office(s) as per TASC SOP 30 for: Amendments to Clinical Research Studies. Amendments to the protocol or other study docs will not be implemented without these approvals.

In the event that a CI needs to deviate from the protocol, the nature of and reasons for the deviation will be recorded in the CRF, documented and submitted to the Sponsor. If this necessitates a subsequent protocol amendment, this will be submitted to the Sponsor for approval and then to the appropriate REC and lead NHS R&D Office for review and approval.

In the event that a serious breach of GCP is suspected, this will be reported to the Sponsor immediately using the form “Notification to Sponsor of Serious Breach or Serious Deviation”.

12.2 STUDY RECORD RETENTION

Archiving of study documents will be carried out as specified in TASC SOP 13: Archiving Clinical Research Documentation and Data. All study documentation will be kept for at least 10 years.

12.3 END OF STUDY

The end of study is defined as last patient last visit (LPLV). The Sponsor, CI and/or the TSC have the right at any time to terminate the study for clinical or administrative reasons.

The end of the study will be reported to the Sponsor and REC within 90 days, or 15 days if the study is terminated prematurely. The CI will ensure that any appropriate follow up is arranged for all participants.

A summary report of the study will be provided to the Sponsor and REC within 1 year of the end of the study

13 REPORTING, PUBLICATIONS AND NOTIFICATION OF RESULTS

13.1 AUTHORSHIP POLICY

Ownership of the data arising from this study resides with the study team and their respective employers. On completion of the study, the study data will be analysed and tabulated, and a clinical study report will be prepared.

13.2 PUBLICATION

The clinical study report will be used for publication and presentation at scientific meetings. Investigators have the right to publish orally or in writing the results of the study.

Summaries of results will also be made available to Investigators for dissemination within their clinical areas (where appropriate and according to their discretion).

13.3 PEER REVIEW

This study has been funded by the British Heart Foundation who have reviewed the grant application.

Additional peer review of the protocol occurs via the Sponsorship Committee. Resulting publications will be reviewed by the referees of the journal to which the paper (and its protocol) will be submitted.

1 ABBREVIATIONS

EC	Electronic Cigarettes
FMD	Flow Mediated Dilation
TC	Traditional Cigarettes
LDL	Low Density Lipoprotein
hs-CRP	High sensitivity C-Reactive Protein
MAR	Missing at random
MedDRA	Medical Dictionary for Regulatory Activities
NHS	National Health Service
PWA	Pulse Wave Analysis
PT	Preferred Term
PWV	Pulse Wave Velocity
SAP	Statistical Analysis Plan
SD	Standard Deviation
SOC	System organ class
SOP	Standard Operating Procedure

2 SUMMARY

Electronic cigarettes (EC) are gaining popularity as an alternative to Traditional Cigarettes (TC). Despite not containing all the harmful substances seen in TC, EC are known to contain impurities that may have a detrimental impact on human health. The effects of ECs compared with TCs on vascular function, inflammation and oxidative stress are unknown. It is increasingly recognised that nicotine itself has significant atherothrombotic effects. Therefore, clinicians are unable to confidently recommend ECs as a method of smoking cessation. We will study 108 smokers with no significant past medical history in a parallel group design randomized to continue their TC, switch to EC plus nicotine or EC minus nicotine for one month. We will measure baseline and post study endothelial function using flow mediated dilatation which will be performed by a single blinded researcher.

3 STUDY POPULATION

Smokers with no clinical diagnosis of established cardiovascular disease

4 STUDY DESIGN

The VESUVIUS trial is an explanatory randomised, single blinded, placebo controlled single-centre study conducted in NHS Tayside to compare the effect of electronic cigarettes with nicotine, electronic cigarettes without nicotine and traditional cigarettes. Participants will be enrolled in this trial for a period of 4 weeks. To ensure balanced assignment across critical variables, a minimisation algorithm will be employed, using baseline age (≤40 years; >40 years), sex (male; female) and smoking pack years (≤20 pack years; >20 pack years).

4.1 PRIMARY OUTCOME

 Change in Flow mediated Dilation (FMD) between the TC group and the EC-nicotine and EC-nicotine free groups

4.2 SECONDARY OUTCOMES

- Change in FMD between EC-nicotine and EC-nicotine free groups
- Change in Pulse Wave Velocity between the TC group, EC-nicotine and the EC-nicotine free groups
- Change in Augmentation Index@75bpm between the TC group, EC-nicotine and the EC-nicotine free groups
- Change in oxidised LDL, hs-CRP, tPA and PAI-1 between the TC, EC-nicotine free and EC-nicotine groups

5 STATISTICS AND DATA ANALYSIS

5.1 SAMPLE SIZE CALCULATION

The primary endpoint measurement is change in brachial artery FMD, which is expressed as the maximum FMD percentage change from baseline. Based on our existing data for this measure (mean response 7.8%, SD=3.5%), and assuming mean FMD reductions of 2%, 1% and 0% in the EC-Nicotine-free, EC-Nicotine, and TC groups respectively with a SD of the change in FMD =3.0% (based on our previous study[1]), and a using a sample size calculation using Linear Contrast Tests[2] a sample size of 36 subjects in each group will have 80% power to detect an improvement in FMD of 2.0% and 1.0% in the EC-nicotine-free and EC-nicotine groups respectively compared to the TC group at 5% significance. Assuming 10%, 15%, and 20% drop-out rates in the TC, EC-nicotine & EC-nicotine-free groups respectively, we will require 135 completed subjects. All drop-outs will be replaced to achieve 36 completed subjects in each group to fulfil the explanatory nature of the trial.

5.2 STATISTICAL ANALYSES

Descriptive statistics in the form of means and standard deviations for continuous variables and percentages and denominators for categorical variables will be tabulated for baseline and at the 4 week visit. The dependent variable will be assessed for approximation to a normal distribution and transformed if necessary. Pre-specified subgroup analyses will be completed by fitting the appropriate interaction term in the regression model and if significant outcomes will be presented separately by level of subgroup. All comparisons will be between treatment groups (EC-nicotine vs EC-nicotine free vs TC) at the final visit (4 weeks), adjusted for the baseline measure of the outcome.

The statistical analysis will be carried out in accordance to TASC SOP 57 "The implementation of statistical analysis in clinical research" by the study team statistician.

5.3 MISSING DATA

The primary analysis will be on a per protocol basis as the trial is essentially explanatory. We will perform an intention to treat analysis as a secondary analysis. The extent of missing data will be examined and the reason for drop-out ascertained and tabulated. Multiple imputation may be used to impute missing values if the assumptions for missing at random (MAR) data are met.

6 GENERAL CONSIDERATIONS

6.1 TIMING & BLINDING OF ANALYSES

The final analysis will be performed after all data have been entered and the database has been locked. Determination of the outcome was blinded. The trial statistician will follow the SAP and so blinding of the statistician is not necessary.

6.2 ANALYSIS POPULATIONS

The primary analysis will be based on the evaluable dataset in an explanatory trial and so is a per-protocol population. A secondary intention-to-treat analysis will also be implemented.

6.3 BASELINE DEMOGRAPHIC, MEDICAL CONDITIONS AND OTHER VARIABLES

Descriptive statistics of the above characteristics will be presented in a table(s).

7 TECHNICAL DETAILS

All analysis will be performed using IBM SPSS 22. Data, analysis programmes and output will be securely backed up. Final analysis programmes will be run without error.

8 PRIMARY ANALYSIS

The FMD response relationship will be assessed by a linear contrast test, and a multiple linear regression on FMD at 4 weeks including the baseline FMD level and experimental group as covariates. The model will also include the minimisation variables; baseline age (≤40 years; >40 years), sex (male; female) and smoking pack years (≤20 pack years; >20 pack years).

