5.5 RANDOMISATION

5.5.1 Randomisation

Randomisation will be carried out in a 1:1 fashion for the 2 randomised arms via a centrally controlled web-based GCP compliant randomisation system, TRUsT, run by Tayside Clinical Trials Unit (TCTU). To ensure balanced assignment across critical variables, a minimisation algorithm will be employed, using baseline age (≤ 40 years; > 40 years), sex (male; female) and smoking pack years (≤ 20 pack years; > 20 pack years). Randomisation will be performed by the PI, researcher or other local delegated individual.

Recruitment will stop when the required number is reached in each arm (maximum 45 per arm)

The TC arm will not be randomised.

To facilitate recruitment and minimise dropouts we propose to recruit the TC smoking arm as a separate non randomised group. Potential participants will be identified and approached in exactly the same ways as for the 2 EC arms. All participants will be asked if they wish to continue to smoke TC or to be randomised to one of the EC arms. This will enable us to recruit volunteers who would find it too difficult to stop their TC for 4 weeks. It will also avoid disappointment for those volunteers who are ready to stop smoking and do not wish to continue with their TC, which has the potential to lead to further dropouts. This is an unblinded study with the exception of the measurement of endothelial function and vascular stiffness which will be performed by a single blinded operator.

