6 STUDY & SAFETY ASSESSMENTS

See Study Matrix, Section 3.3.

Flow Mediated Dilatation

Participants will be asked to fast from midnight the night before their visits, with the visit being performed in the morning. Participants who are electing to take part in one of the 2 randomized arms will also be asked not to smoke for 4 hours prior to their visits. Participants electing to take part in the tobacco cigarette arm do not have to withhold cigarettes for 4 hours but they will be asked to keep their smoking practises consisted before both visits. Endothelial function will be measured non-invasively at 0 and 1 month using the standard technique of flow mediated dilatation (FMD) of the brachial artery in response to hyperemia and to sublingual GTN. Brachial artery diameter and flow are determined by M mode and Doppler ultrasound as described by us previously³¹. FMD measurements are represented as change in arterial diameter from baseline. We will follow established protocols³². FMD is the technique we used recently to show a beneficial effect of allopurinol on endothelial function in subjects with chronic kidney disease³³ and in coronary artery disease³⁴. Our in house CV for FMD measurements is 3%. The FMD will be measured by a single experienced operator who will be blinded to treatment arms.

Vascular Stiffness

Pulse wave velocity (PWV) and pulse wave analysis (PWA) measurements including augmentation index corrected for heart rate (Aix@75) will be performed at baseline and 4 weeks using Sphygmocor™ as previously detailed³⁵. The FMD, PWV and PWA will be measured by a single experienced operator who will be blinded to treatment arms. These two measures have been validated as markers of cardiovascular risk³⁶.

Blood tests

The following blood tests will be carried out:

- 1) Oxidised LDL
- 2) High-sensitivity CRP
- 3) Platelet reactivity
- 4) Peripheral blood mononuclear cells for Oxidative stress NRf2 expression only (30 patients only, to be randomly selected).

Blood will also be stored, with patient consent, for future biomarker analysis.

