8.1 SECONDARY ANALYSES

- 1) Changes in Oxidised LDL between baseline and Visit 4
- 2) Changes in High-sensitivity CRP between baseline and Visit 4
- 3) Changes in Tissue Plasminogen Activator between baseline and Visit 4
- 4) Changes in Platelet Activation Inhibitor-1 (PAI-1) between baseline and Visit 4

Subgroup analyses: interaction terms of treatment in men vs women, upper tertile baseline smoking versus lower tertile comparisons for all primary and secondary endpoints All secondary outcomes will be analysed in the same manner as the primary outcome. Results will be presented as between group differences in measured parameters between the baseline and final visit.

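### As the SAP naturally reads, the standard error of the only randomised comparison (EC-nicotine vs EC-nicotine free) is pooled with the non-randomised TC arm, and is correct only if TC has the same residual SD

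*SAP*

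**What the plan says.** Only the two EC arms are randomised, 1:1 (Protocol 5.5.1). Of the third group the same section says "The TC arm will not be randomised"; participants choose whether to join it. The SAP's own summary describes all three groups as randomised. This point follows the protocol, and the two texts should be reconciled.

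SAP 4.2 lists "Change in FMD between EC-nicotine and EC-nicotine free groups" as a secondary outcome. The primary model in SAP 8 is "a multiple linear regression on FMD at 4 weeks including the baseline FMD level and experimental group as covariates", with the three minimisation factors added. SAP 8.1 says "All secondary outcomes will be analysed in the same manner as the primary outcome", and SAP 5.2 describes all comparisons as being among the three groups at 4 weeks, adjusted for baseline. No sentence says which participants enter the model for the comparison of the two EC arms.

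The only distributional check is for normality, with transformation if needed (SAP 5.2). No variance check, robust standard error or model restricted to the EC arms is mentioned.

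Protocol 6 asks the EC arms not to smoke for 4 hours before visits, whereas "Participants electing to take part in the tobacco cigarette arm do not have to withhold cigarettes for 4 hours". TC participants are asked instead to smoke in a similar way before both visits. The sample size in SAP 5.1 uses one SD of change, 3.0, for all three arms.

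**The concern.** An ordinary linear regression on three groups uses one residual variance for every contrast. With equal group sizes, about a third of the information behind the standard error of EC-nicotine vs EC-nicotine free then comes from TC participants, who play no part in that comparison.

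Equal variance across arms is not assured. TC participants may smoke shortly before measurement, which could make their FMD more variable. The EC arms change behaviour, with uptake that may vary, which could make theirs more variable. If TC is the less variable arm, the interval for the nicotine comparison is too narrow and false positives rise. If TC is the more variable arm, the interval is too wide and power falls. The same pooling affects the primary contrast, EC-nicotine free vs TC, in the opposite direction. At stake is the calibration of the one comparison that rests on randomisation and isolates nicotine.

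**Working it through.** **Inputs.** From SAP 5.1: 36 completers per arm; 5% significance, taken as two-sided; SD of FMD 3.5; SD of change 3.0; expected gains of 2.0 points (EC-nicotine free) and 1.0 point (EC-nicotine) over TC, so 1.0 point between the EC arms. Assumed, because the documents do not give it: r, the ratio of the TC residual SD to the EC residual SD. Group is taken as a three-level factor.

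**The plan's own figure.** SAP 5.1 states that "a sample size of 36 subjects in each group will have 80% power". For the linear contrast (−1, 0, 1) with a common SD, n = 2 × [SD × (1.960 + 0.842) / difference]² = 2 × (3.0 × 2.802 / 2.0)² = 35.3, rounded up to 36. The noncentral t with 105 df gives 80.0% power. The figure is reproduced, and it rests on equal SDs.

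**Residual SD after baseline adjustment.** The implied correlation between baseline and 4 weeks is 1 − 3.0² / (2 × 3.5²) = 0.633. The residual SD is 3.5 × √(1 − 0.633²) = 2.71.

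**Randomised contrast.** With equal n, the pooled variance averages (1 + 1 + r²)/3 times the EC variance, while the true variance of the contrast involves the EC arms only. So

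pooled SE / true SE = √((2 + r²)/3),

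and the approximate two-sided error is 2Φ(−1.96 × ratio). The simulated column fits the full SAP 8 model (group, baseline, three minimisation factors) with 36 per arm.

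| r | SE ratio | Error, formula | Error, simulated |
|---|---|---|---|
| 0.67 | 0.90 | 7.7% | 7.3% |
| 0.9 | 0.97 | 5.8% | 5.5% |
| 1 | 1.00 | 5.0% | 4.9% |
| 1.1 | 1.03 | 4.3% | 4.0% |
| 1.33 | 1.12 | 2.8% | 2.8% |
| 1.5 | 1.19 | 2.0% | 2.3% |

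Repeat simulations differ by a few tenths of a percentage point. The same regression restricted to the two EC arms gave about 5% at every r. Unequal completers (41/38/36) changed little: 7.5% at r=0.67 and 2.1% at r=1.5.

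**Power for 1.0 point between the EC arms.** At r=1, power is 33% in the three-arm model and 32% in the EC-only model. At r=1.5 it is 21% and 32%.

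**Contrast of EC-nicotine free with TC.** The ratio is √[((2 + r²)/3) × 2/(1 + r²)]. This is 1.10 at r=0.5 and 0.93 at r=1.5, or about 3.2% and 6.7% error by the same approximation.

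**Shared baseline slope.** Giving TC a slope of 0.3 or 0.9 against 0.63 in the EC arms left the error of the randomised contrast at 4.8–5.0%. The common slope is not part of the problem.

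**Cost if variances are equal.** Residual df fall from 108 − 7 = 101 to 72 − 6 = 66. The critical t rises from 1.984 to 1.997, which alone adds 0.6%. Estimating the covariate effects from fewer participants adds the rest: mean interval width goes from 2.58 to 2.62, about 1.6%.

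**The case against.** The strongest reply is that everything turns on r, which the documents do not supply. The two reasons for unequal variance pull in opposite directions, so even its sign is unknown. TC participants are asked to keep their smoking consistent before both visits and the model adjusts for baseline FMD, which weakens the case for a more variable TC arm. Within 10% of equal SDs the standard error is off by only about 3% and the simulated error stays between about 4.0% and 5.5%. All of this stands. A reader might infer that the planned test is known to be anti-conservative, or that the estimate itself is distorted by TC. The documents support neither: they show no difference in variance, and the fault would lie in the standard error, not the estimate.

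It can also be said that the SAP never states that the EC comparison comes from the three-arm fit; the same manner could mean the same covariates. That is fair. The three-arm reading is the natural one from SAP 5.2, 8 and 8.1 together, but it is an inference.

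Lastly, this is a secondary outcome with larger limits. About 142 per arm would be needed for 80% unadjusted power at 1.0 point: 2 × (3.0 × 2.802 / 1.0)² = 141.3. The per-protocol primary analysis and the replacement of drop-outs already dilute the protection of randomisation, and an EC-only model does not repair that. This is right, and it limits the weight of the point without removing it.

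**Conclusion.** The point holds in a conditional form. As naturally read, the plan makes the precision of its only randomised comparison depend on the variance of a self-selected arm measured under a different smoking rule, and it has no safeguard if that variance differs. Over an assumed r from 0.67 to 1.5, the error of a nominal 5% test runs from about 7.3% down to 2.3%; close to r=1 the effect is small. This rests on 36 per arm, the plan's SDs of 3.5 and 3.0, and group fitted as a factor. Since the documents neither show nor rule out unequal variances, this is a cheap improvement to the SAP rather than a demonstrated error. It makes the randomised comparison valid whatever the TC variance proves to be.

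**What to change.** In SAP 8 and 8.1, state that EC-nicotine vs EC-nicotine free, for FMD and every secondary outcome, is estimated in a regression restricted to the two randomised arms, with the same baseline value and minimisation factors. For contrasts with TC, keep the three-arm model and report heteroscedasticity-robust (HC3) standard errors. Their simulated error was 4.2–4.7%, slightly conservative. Confirm that the software named in SAP 7 can produce them.

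This takes two sentences and one extra model run per outcome. If variances are equal, the price is the 1.6% wider interval and about 1 percentage point of power shown above. The change should be fixed before the data are analysed, so that the choice of fit cannot follow the result.

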8.1 SECONDARY ANALYSES

- 1) Changes in Oxidised LDL between baseline and Visit 4
- 2) Changes in High-sensitivity CRP between baseline and Visit 4
- 3) Changes in Tissue Plasminogen Activator between baseline and Visit 4
- 4) Changes in Platelet Activation Inhibitor-1 (PAI-1) between baseline and Visit 4

Subgroup analyses: interaction terms of treatment in men vs women, upper tertile baseline smoking versus lower tertile comparisons for all primary and secondary endpoints All secondary outcomes will be analysed in the same manner as the primary outcome. Results will be presented as between group differences in measured parameters between the baseline and final visit.

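### The smoking subgroup contrast of upper against lower tertile gives up roughly a fifth to a third of the available precision, and about 14 interaction tests have no multiplicity statement or exploratory label

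*SAP*

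**What the plan says.** SAP 8.1 names two subgroup factors. Sex is handled through "interaction terms of treatment in men vs women", and smoking through "upper tertile baseline smoking versus lower tertile comparisons for all primary and secondary endpoints". The SAP does not say which smoking measure is meant, where the tertile cut-points come from, or what happens to the middle tertile.

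SAP 5.2 (and Protocol 8.2, in the same terms) fits an interaction term in the regression model and adds: "if significant outcomes will be presented separately by level of subgroup".

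The endpoints are in SAP 4.1 and 4.2. The primary is FMD. The secondaries are a further FMD contrast ("Change in FMD between EC-nicotine and EC-nicotine free groups"), pulse wave velocity, augmentation index and four blood markers ("Change in oxidised LDL, hs-CRP, tPA and PAI-1 between the TC, EC-nicotine free and EC-nicotine groups"). That makes seven distinct outcome variables.

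Neither document gives a significance level for interaction tests, a multiplicity rule or an exploratory label. The 5% level appears only in the sample size section.

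**The concern.** Smoking exposure is available as a quantity. Smoking history is taken at baseline (Protocol 3.3), and pack-years must be worked out for the minimisation cut at 20 (Protocol 5.5.1) and for the primary model (SAP 8). Reducing it to a comparison of two outer thirds loses information in a subgroup analysis that already has little power.

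The second issue is what readers will see. Many interactions are tested without any stated error control, and the by-level results appear only for those that cross a threshold. With small cells, the estimates selected in this way tend to be exaggerated, and the SAP does not commit to showing the rest beside them.

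**Working it through.** **Inputs.** From SAP 5.1: 36 completers per group (108 in all), SD of change in FMD 3.0, planned difference 2.0 points between EC-nicotine free and TC, 80% power, 5% significance. From SAP 4.1, 4.2 and 8.1: seven outcome variables and two subgroup factors. Assumed: 5% two-sided per interaction test, and the shape of the smoking distribution.

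**1. The plan's own figure.** A linear contrast (-1, 0, 1) over three groups reduces to two means: n = 2 × (1.96 + 0.842)² × 3.0² / 2.0² = 35.3, so 36 per group. A noncentral t with 105 df gives power 0.800. The stated sample size is reproduced at two-sided 5%. It covers the main comparison, not the subgroups.

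**2. How many enter the smoking contrast.** 108 × 2/3 = 72 completers, and 36/3 = 12 per arm per tertile if smoking is similar across arms. The TC arm is self-selected (Protocol 5.5.1), so actual cells may be unequal.

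**3. Efficiency against a continuous interaction.** Take N participants, residual variance σ² and a linear effect of smoking in SD units. The continuous slope has variance σ²/N. The difference between two outer-third means has variance 2σ²/(N/3) = 6σ²/N. Dividing by the distance d between those means gives a slope variance of 6σ²/(N d²). Relative efficiency is therefore d²/6. The same ratio applies within each arm and so to the interaction.

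| Assumed shape of smoking | d (SD units) | d²/6 |
|---|---|---|
| Normal | 2.18 | 0.79 |
| Lognormal, log-SD 0.3 | 2.11 | 0.74 |
| Lognormal, log-SD 0.5 | 1.98 | 0.65 |

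The loss is 21% to 35% of the effective sample. Other shapes widen the range: 0.89 for a uniform and 0.61 for a shifted exponential.

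**4. Power in context.** For EC-nicotine free against TC, the tertile interaction in FMD has standard error 3.0 × √(4/12) = 1.73. The smallest interaction detectable with 80% power is 2.80 × 1.73 = 4.85 points, against a planned main effect of 2.0. A single such contrast reaches p<0.05 only if the estimate exceeds 1.96 × 1.73 = 3.4 points. Baseline adjustment may reduce these figures somewhat.

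**5. Number of tests.** 2 factors × 7 outcomes = 14. If independent, the chance of at least one p<0.05 under no interaction is 1 - 0.95^14 = 51.2%. With only FMD and the four blood markers it is 1 - 0.95^10 = 40.1%. With the second FMD contrast counted as an eighth endpoint it is 1 - 0.95^16 = 56.0%.

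Outcomes measured on the same people are probably correlated. A simulation (4,000 runs per setting, 36 per arm, equal sex split, equal tertiles with the middle third left out, equal pairwise correlation between outcomes) gave, for seven endpoints:

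| Correlation | One 2-df test per endpoint and factor | Each EC arm tested against TC |
|---|---|---|
| 0 | 51% | 74% |
| 0.2 | 48% | 71% |
| 0.3 | 47% | 70% |
| 0.5 | 42% | 62% |

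The SAP does not say which form of test is used.

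**The case against.** The strongest reply is that these are pre-specified secondary subgroup analyses in a study that describes itself as preliminary (Protocol 1.1), so the point is one of good practice. That stands, and it limits the severity. Four stronger readings are tempting, and the documents do not support them.

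- **A false subgroup finding is more likely than not.** The figure passes 50% only narrowly, with 14 independent tests at an assumed 5%. Plausible correlation brings it to 42-48%, and five endpoints to 40% or less. It exceeds 50% under correlation if pairwise contrasts are tested, or if an eighth endpoint is counted and correlation is low; the SAP specifies neither.
- **The tertile choice or the display rule causes the false positives.** Neither changes the type I error of an interaction test or the number of tests. The count of uncorrected tests does that.
- **A third of participants is discarded.** The SAP names a contrast and does not say that the middle tertile is excluded from the model. A three-level factor would keep those people for covariate and residual-variance estimation, though they would still add nothing to the contrast itself. Under normality the loss is 21%, not a third.
- **Null interactions will go unreported.** SAP 5.2 makes only the by-level breakdown conditional. Asking for a significant interaction before showing strata is also a recognised guard against reading separate subgroup p-values. What remains is that the SAP makes no commitment to report all the interaction estimates.

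It is also fair that the efficiency figures rest on assumed distributions and on linearity. Entry requires at least 15 cigarettes a day (Protocol 4.2), so cigarettes per day would be truncated.

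**Conclusion.** The point holds as a minor one with two separate parts.

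First, the upper-versus-lower contrast is a less efficient way to ask whether smoking exposure modifies the effect. It keeps about 79% of the efficiency of a continuous interaction if smoking is normal and about 65-74% if right-skewed, provided that the modification is linear. The sex subgroup and all main analyses are untouched.

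Second, the interaction tests carry no multiplicity statement or exploratory label. The chance of at least one nominally significant interaction under the null is roughly 40-50% with one test per endpoint at an assumed 5%, and 62-74% if each EC arm is tested against TC. The by-level results shown would be those that passed the threshold. The case for full reporting does not depend on which side of 50% the figure falls.

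**What to change.** In SAP 8.1, replace the tertile contrast with a group × continuous baseline smoking interaction fitted on all participants. Name pack-years as the measure, since it is already needed for minimisation. Plot tertile means only to check linearity.

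In SAP 5.2, replace the conditional display rule with a commitment to report every interaction estimate and its 95% CI whatever the p-value, labelled exploratory, with the number of tests stated. Say whether each interaction is one overall test or a set of pairwise contrasts. Align the matching sentence in Protocol 8.2.

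The cost is SAP wording, one extra table and a linearity assumption that the plot can check. No new data are needed. The reporting change leaves the number of false positives as it is: it lets readers see the whole set of results instead of a selected part.
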